### **Zinc in T lymphocytes activation and exhaustion**

Several studies have indicated that T cells have a role both in the early immune response against SARS-CoV-2 and that a functional memory is generated (19). In this context, zinc is known to affect T lymphocyte maturation, differentiation and cytokine production (2,4,7). Activated T cells are known to increase zinc content (20). On the one hand, zinc has been shown to be required for the correct TCR signalling by modulating Lck and Zap-70 activity (20). Our team has demonstrated that zinc positively potentiates the three main signalling pathways, AP-1, NF- $\kappa$ B and NFAT1 (21). In addition we have described that the knock down of Zip6, a zinc transporter up regulated early during cell activation, alters zinc entry and dramatically impairs activation of Jurkat T cells (21). Moreover, recent studies on CD8+ T cell dysfunction during cancer and chronic infections have started to elucidate the transcriptional pathways involved in this phenomenon and zinc homeostasis has emerged again as a key element. Thus, metallothioneins 1 and 2 levels and zinc dependent transcription factors are differentially expressed in exhausted CD8+ cells (22,23,24). Nonetheless, there are no studies investigating whether zinc supplementation/chelation might directly affect the CD8+ dysfunctional profile and how these learnings could be translated into novel therapeutic approaches for these diseases including the current COVID-19 pandemic.

### **Zinc in B lymphocyte function**

B lymphocytes are key players for an effective immune response against SARS-CoV2. Antibodies against the spike and nucleocapsid proteins of the virus are detectable from approximately 6 days after PCR confirmation of infection. A decline of anti-SARS-CoV-2

serum IgG levels occurs beyond 20 days post-diagnosis and it is still unclear how long immunity to SARS-CoV-2 lasts after recovery from infection. Importantly, it has been shown that zinc transporters (Zip7 and Zip10) are essential in B cell function. B cells activation and plasma cell differentiation depends on zinc signalling (25,26). Nutritional zinc status is an important factor determining antibody production given its action on both, B-cells and CD4+ T lymphocytes. Thus, ZD has been shown in mouse models to lower humoral immune response (26).

In summary, there are several cross talks between zinc homeostasis and immune function. Moreover zinc has an antiviral activation against certain viruses. All these connections together with the association found between low plasma zinc levels and COVID-19 severity suggest that zinc supplementation might be an important therapeutic tool in COVID-19 patients. A clinical trial based on zinc nutritional immunity together with a deeper knowledge of the impact of zinc supplementation in immune cells will be useful for the current COVID-19 pandemic and other infection diseases

### **3. PRELIMINARY RESULTS:**

Our preliminary results are shown in the work entitled “**Low zinc levels at clinical admission associates with poor outcomes in COVID-19**” (13) which is the result of a tight collaboration between the laboratory of [name] (Hospital del Mar) and those of [name] and [name] (both at DCEXS, UPF).

This work aimed to focus clinical attention on serum zinc content (SZC) in COVID-19 patients. Our analysis showed a robust correlation between low SZC with COVID-19

severity and mortality. The cause is likely to be a combination of immune system imbalance and a direct benefit of viral replication.

A summary of the results obtained:

- In our retrospective observational study with 249 COVID-19 patients, **23% of the patients had at admission SZC lower than 50µg/dl**, the cutoff associated with ZD and development of clinical signs.
- Our study showed that **low SZC correlates with higher IL-6 and C-reactive protein at admission**, higher peak IL-6 during the episode.
- We detected in the low SZC group that subjects needed higher time to recover (25 days) versus the control group (8 days). In the same direction, the **mortality in low SZC patients was higher (21%) than in the control group (5%)** with normal zinc concentration.
- **SARS-CoV2** Infections in cell culture demonstrated that **low zinc levels favors SARS-CoV2 viral expansion** in the infected cells.

These results highlighted the urgent need to start clinical trials supplementing with zinc low SZC patients at admission to reestablish zinc homeostasis in order to study the cause-effect association between zinc nutritional status and COVID-19 progression. We expect with this new project that zinc supplementation in low SZC COVID-19 patients will

balance what has been called the cytokine storm caused by SARS-CoV-2 and as a consequence will reduce COVID-19 severity and mortality.

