### **Study Endpoints**

#### **Primary Endpoints**

- Number of days since admissions to clinical recovery
- Change in IL-6 levels from baseline to Week 2.
- Percentage of patients with disease progression by Week 2 based on WHO 9-point ordinal scale

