#### **Secondary Endpoints**

- Change in Covid-19 signs/symptoms: dyspnea, diarrhea, temperature, neutrophil count... at Week 2

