### **Task 1.1.1 Visits and sample collection**

1.- Visit 1. Screening. Randomization. Baseline. Phase / Visit 0 or 1 ( Day 1 or up to 1 day  
Prior to Baseline/Randomization; In Person)

Visit performed at admission (+1). Written informed consent obtained. Medical history.  
Vital signs assignment. Clinical labs (CBC, CMP, CRP, ferritin, D-dimer,IL-6, zinc)

2.-Visit 2 / Week 1 (Day 7  $\pm$  2 days)

A complete record of AEs and concomitant therapies will be taken into account. 3.-

Visit 3 / Week 2 (Day 14  $\pm$  2 days), End of Treatment

A complete vital sign assessment (sitting blood pressure, heart rate, respiratory rate, O2  
sat, and oral temperature) review and record AEs and concomitant therapies, clinical  
labs (stated above) and PBMCs. Collect blood samples for future studies.

4.-Visit 4 / End of Study (Day 28  $\pm$  4 days)

Clinical labs (stated above) and PBMCs. Collect blood samples for future studies.

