### **Statistical analysis**

**Randomization: Subjects** will be randomized in a 1:1 ratio to:

- 83.91 mg zinc acetate (Zinc+NM) QD + standard of care for 2 weeks
- Standard of care for 2 weeks

**Determination of sample Size:** Sample size calculations are aimed at comparisons of days to clinical recovery between zinc supplementation and standard of care alone. Assuming alpha = 0.05 and a 10% dropout rate, randomization of 60 subjects will

provide 80% power to detect a difference in time to recovery between arms of 3 days assuming a SD of 4 days. This sample size will also provide at least 80% power to detect a change in percentage of people with clinical progression of 5% based on an estimated

clinical progression rate of 20% in the standard of care arm.

**Analysis Populations:** The analysis population for efficacy will be per protocol which includes all randomized subjects who complete 2 weeks of therapy and/or return for Week 2 visit. All safety analyses will include all randomized subjects who are

administrated at least 1 packet of the investigational product.

**Baseline Characteristics:** Demographics and Baseline characteristics will be summarized descriptively by group and overall using per protocol population. The following Baseline

characteristics will be summarized: sex, race, age, comorbidities, ethnicity

**Clinical Laboratory Assessments:** Blood chemistry, hematology parameters will be summarized at Baseline as well as visit 3 and 4. Laboratory values at Baseline and subsequent changes in laboratory values will be summarized descriptively overall and

by therapy group.

**Vital signs:** Vital sign measurements will be summarized at Baseline, Week 2 and Week 4. In addition, changes from Baseline to Week 2 or 4 will be summarized. For each summary the number, mean, median, standard deviation, minimum, and maximum

values will be presented overall and by therapy group.

**Safety Analyses:** All safety analyses will be based on the Safety Population, comprising all subjects who are randomized to the therapy group and subsequently receive at least one packet of investigational product. Safety assessments will be analyzed by frequency of events/abnormalities for categorical values or summarized using descriptive statistics

(mean, standard deviation, median, range, and number of observations).

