**Task 3.2 Characterization of machinery for cellular zinc handling in PBMCs from SARS-CoV-2 infected mice. from mice**

We will study the expression in PBMCs from SARS-CoV-2 infected mice at 7 days post infection (objective 2.1) in the three groups of mice (deficient, adequate and supplemented diet).

**EO:** Zinc plasma levels are very dependent on inflammatory signalling. We expect to find certain genes differentially regulated depending on the nutritional zinc status and COVID-19 progression.

**D4:** A novel and reliable diagnostic tool in the hospitals to check zinc nutritional status and define therapeutic strategies with COVID-19 patients and for other infectious diseases.

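### The plan reads a null clinical result as proof that low zinc is a consequence of inflammation, but specifies no between-arm estimate of whether the regimen raised zinc

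*Combined protocol and SAP*

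**What the plan says.** The preliminary results section gives the reason for the trial: supplement patients with low zinc at admission "to reestablish zinc homeostasis in order to study the cause-effect association between zinc nutritional status and COVID-19 progression".

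The primary endpoints are "Number of days since admissions to clinical recovery", "Change in IL-6 levels from baseline to Week 2" and "Percentage of patients with disease progression by Week 2 based on WHO 9-point ordinal scale". The secondary endpoint is "Change in Covid-19 signs/symptoms: dyspnea, diarrhea, temperature, neutrophil count... at Week 2", an open list that does not name zinc. The safety endpoint is adverse events. The efficacy outcomes in Task 1.1.2 are clinical recovery, the WHO scale and IL-6.

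Serum zinc is nevertheless collected. Task 1.1.1 lists, at Visit 1, "Clinical labs (CBC, CMP, CRP, ferritin, D-dimer,IL-6, zinc", and repeats the same panel at Visit 3 (Week 2) and Visit 4 (Day 28) in both arms.

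Under Clinical Laboratory Assessments the plan covers blood chemistry and haematology at baseline and Visits 3 and 4, and says that "subsequent changes in laboratory values will be summarized descriptively overall and" by therapy group. Zinc is not named, and no arm difference, confidence interval or test is specified.

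The Limitation paragraph that closes the statistical section says that finding no benefit would mean the low zinc seen in patients with a worse course is the result of their inflammatory state. It attaches no condition about what happened to zinc during the trial.

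**The concern.** The Limitation paragraph reasons from no clinical benefit to zinc being a consequence rather than a cause. A step is missing between the two: the supplemented arm must have had higher zinc than the control arm. If the arms did not separate, the trial did not vary zinc status, and a null clinical result says nothing about whether low zinc drives outcome. Following the paragraph as written could therefore lead to a wrong causal statement in the trial report.

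A change from baseline within the supplemented arm cannot supply the missing step. The Zinc and inflammation section says IL-6 lowers zinc availability, and the expected outcome under Task 3.2 says "Zinc plasma levels are very dependent on inflammatory signalling". On the documents' own reasoning, serum zinc may climb in controls as inflammation settles. Only the comparison of randomised arms isolates what the regimen did.

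**Working it through.** **Side-by-side reading.** Three statements have to fit together.

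1. Purpose: change zinc status and see what happens to the disease (preliminary results).
2. Planned inference from a null: low zinc is a consequence of inflammation (Limitation paragraph).
3. Planned evidence on whether zinc status changed: descriptive laboratory summaries by group, zinc not named (Clinical Laboratory Assessments), and PBMC zinc-transporter and metallothionein expression in both groups at admission and 2 weeks, to be correlated with serum zinc (objective 3 and Task 3.1).

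Statement 2 needs an estimated between-arm difference in zinc. Statement 3 supplies the raw material but no such estimate.

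**The plan's own sample-size figure.** Inputs from the statistical section: N = 60, 1:1, 10% dropout, alpha 0.05 (taken as two-sided), difference 3 days, SD 4 days. Evaluable per arm: 60 × 0.9 / 2 = 27.

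Power = Φ(3 / (4 × √(2/27)) − 1.96) = Φ(2.756 − 1.960) = Φ(0.796) = 78.7%, which agrees with the stated 80%. So 27 per arm is a fair basis for the zinc calculation.

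**What 27 per arm can show on zinc.** Model: Week-2 serum zinc by arm, adjusted for admission zinc. The documents give neither an SD for serum zinc nor a correlation between admission and Week 2. Results are therefore in units of the Week-2 SD, with the correlation r assumed to lie between 0.3 and 0.7.

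- 95% CI half-width = t(0.975, 52) × √(2/27) × √(1 − r²) = 2.007 × 0.272 × √(1 − r²) = 0.546 × √(1 − r²).
- Difference detectable with 80% power (t-test) = 0.777 × √(1 − r²).

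| r (assumed) | √(1 − r²) | CI half-width (SD) | Detectable at 80% power (SD) |
|---|---|---|---|
| 0.3 | 0.954 | 0.52 | 0.74 |
| 0.5 | 0.866 | 0.47 | 0.67 |
| 0.7 | 0.714 | 0.39 | 0.55 |

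Without adjustment the detectable difference is 0.78 SD. For an assumed SD of 10, 15, 20 or 25 µg/dl, that is 7.8, 11.7, 15.5 or 19.4 µg/dl.

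For a true separation of 0.5 SD, power is only about 47%, 55% and 71% at r = 0.3, 0.5 and 0.7. A CI that includes zero would therefore often not show that the arms failed to separate.

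**How many patients have a deficit to correct.** The inclusion criteria shown do not require low zinc. In the prior cohort 23% were below 50 µg/dl at admission: 0.23 × 60 = 13.8, or about 14 patients and 7 per arm. With 7 per arm the detectable difference is about 1.5 SD (normal approximation) to 1.6 SD (t-test). A comparison of the share crossing 50 µg/dl has no useful power.

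**The case against.** The strongest defence is that the trial does not need a zinc endpoint to meet its primary objective. That objective is the effect of supplementation against control on IL-6, recovery and progression, and randomisation answers it whatever serum zinc does. The sentence about re-establishing zinc homeostasis is motivation in the preliminary results, not a listed trial objective. This stands. It confines the point to conclusions about zinc status, which is the kind of conclusion the Limitation paragraph draws.

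A reader might go further and infer that no result of the trial, positive or null, could be attributed to zinc status. The documents do not support that. Serum zinc is drawn in both arms, laboratory changes are shown by therapy group so the control arm's rise would be visible, and PBMC zinc markers are taken in both groups. The Cellular zinc homeostasis section ranks leukocyte metallothionein expression among the most reliable measures of body zinc. What is missing is a pre-specified estimate and a condition on its use, not the measurement.

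A reader might also want a symmetric rule: attribute any clinical result to zinc if the zinc CI excludes zero. That would be unsound. A two-sided rule would be satisfied by lower zinc in the treated arm. If the regimen lowered IL-6 by any route, zinc could rise as a result. Separation among patients who were never deficient would not be a correction of zinc status.

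The absence of zinc at Day 7 is not a defect that the documents establish. No laboratory draw is listed at that visit. The 8-day recovery seen in the prior cohort's control group sits beside 25 days in the low-zinc group, for whom Week 2 comes before typical recovery. Nor do the documents describe home dosing, so missed doses at home cannot be offered as a reason for non-separation.

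**Conclusion.** The point holds in a limited form. The plan draws a causal conclusion about zinc from a null clinical result without specifying the between-arm estimate that this conclusion requires. Because the conclusion is written into the plan, this is more than missing detail.

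The estimate is feasible at N = 60 on planned samples, with no change to sample size or alpha. It will be imprecise: a half-width of 0.52 to 0.39 SD, and 80% power only for separations of about 0.74 to 0.55 SD. These figures assume 27 patients per arm with a Week-2 sample, a two-sided 5% level and a correlation of 0.3 to 0.7. Smaller real separations may be missed, so a CI that includes zero must be read by its width.

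Higher zinc in the supplemented arm is necessary for attributing a clinical effect, or its absence, to zinc status, but it is not sufficient. If the prior cohort is a guide, most enrolled patients will have no deficit below 50 µg/dl, which makes an unconditional reading of a null less safe still.

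**What to change.** 1. Add a secondary or pharmacodynamic endpoint: the between-arm difference in serum zinc at Week 2, by ANCOVA on admission zinc, in all randomised patients with a Week-2 sample, with 95% CI. Name zinc in the laboratory summary. Report the PBMC metallothionein data by arm as support.

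2. Reword the Limitation paragraph. A null clinical result is read as evidence about zinc status only if the CI shows higher zinc in the supplemented arm. Otherwise the trial is reported as inconclusive on zinc status, with the width of the CI discussed.

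3. State that separation is necessary but not sufficient to attribute a clinical effect to zinc status. State also that few patients may be deficient at entry, so any share moving from below to at or above 50 µg/dl is descriptive only.

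The cost is SAP wording and one model on data already to be collected. The downside is one more secondary analysis and a more cautious conclusion. The change should be made before zinc or outcome data are examined by arm.

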## **METHODOLOGY:**

The methodology is divided into objectives, subobjectives and tasks. Expected outcomes (EO), deliverables (D) and limitations are described for each task.

- **To study the impact of zinc supplementation on COVID-19 progression.**
- **To carry out the clinical trial with COVID-19 patients (Subproject**

### **1) Clinical trial objectives**

#### **Primary objective**

To evaluate the effectiveness of oral zinc supplementation (83.91 mg zinc acetate) Zinc+NM QD (80mg Zn2+) QD as compared to placebo as compared to control group without zinc supplementation to reduce IL-6 increase in the course of SARS-CoV-2 infection, to decrease days to clinical recovery and to decrease the percentage of people with COVID-19 who have disease progression by Week 2, defined as inpatients, worsening of  $\geq 1$  level on the WHO 9-point ordinal scale

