### **Study Design**

This is a randomized, open-label clinical study evaluating the effectiveness of zinc supplementation as compared to standard of care on need disease severity and on IL-6

levels in people with COVID-19. Subject eligibility will be based on inclusion and exclusion criteria

**Population of study:** Sixty eligible adult subjects at one clinical site in Spain (Hospital del Mar) will be randomized in a 1:1 ratio to:

- ~~Zinc acetate 80mg QD~~ 83.91 mg zinc acetate (Zinc+NM) QD + standard of care for 2 weeks
- Standard of care for 2 weeks

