**Study phases (4 weeks):**

- Screening + Randomization + Baseline Visit (Visit 1, same day as or up to 1 day before Baseline Visit)
- Treatment (Day 1 to Day 14) Starting on Day 1 (Baseline/Randomization), Randomized subjects will receive 80mg zinc for 2 weeks. Day 7 for clinical state. Day 14 follow up visit.
- Follow up phase : Day 28 for clinical state.

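### The zinc regimen is stated inconsistently: 83.91 mg of zinc acetate in some places and 80 mg of zinc in others, a gap of about 5% or about threefold depending on how the 80 mg is read

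*Combined protocol and SAP*

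**What the plan says.** Four sections of the combined protocol and SAP state the regimen.

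- **Primary objective:** "oral zinc supplementation (83.91 mg zinc acetate) Zinc+NM QD (80mg", where the 80 mg is given as Zn2+. One once-daily regimen carries both a salt weight and an amount of zinc ion.
- **Study Design:** the active arm is 83.91 mg of zinc acetate (Zinc+NM) once daily plus standard of care. Just before it, a figure of 80 mg of zinc acetate once daily is struck through.
- **Study phases (4 weeks):** "Randomized subjects will receive 80mg zinc for 2 weeks". This sentence is not struck through. It names zinc rather than zinc acetate, and it gives no frequency.
- **Statistical analysis, Randomization:** "83.91 mg zinc acetate (Zinc+NM) QD + standard of care for 2 weeks".

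The dosage unit appears only in the definition of the safety population, as subjects "administrated at least 1 packet of the investigational product". No section gives the salt form (anhydrous or dihydrate), the elemental zinc in a packet, or the number of packets in a daily dose.

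**The concern.** Zinc acetate is only partly zinc by mass, so a weight of the salt and a nearly equal weight of zinc cannot describe the same dose. Someone working from Study phases and someone working from the arm definition could, on a literal reading, arrive at different amounts of zinc.

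Zinc is the only intervention tested, and three uses of the results need a known dose. The first is the adverse-event summary by therapy group. The second is the interpretation of the efficacy result, including the statement under Limitation that a null finding would mean low zinc is a consequence of inflammation. The third is deliverable D1, a guideline on zinc supplementation for hospital patients.

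**Working it through.** **Inputs from the documents.** Salt weight 83.91 mg (Primary objective, Study Design, Statistical analysis); 80 mg as Zn2+ (Primary objective); 80 mg as zinc (Study phases); 14 days of treatment.

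**Assumptions, not in the documents.** Atomic masses Zn 65.38, C 12.011, H 1.008, O 15.999. Both salt forms are computed because neither is named. The Study phases figure is taken as a daily amount, in line with the once-daily dosing stated elsewhere.

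**Step 1. Zinc fraction of the salt** (mass of Zn divided by formula mass)

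- Anhydrous: 65.38 + 4 × 12.011 + 6 × 1.008 + 4 × 15.999 = 183.47; 65.38 / 183.47 = 35.6%.
- Dihydrate: 183.47 + 2 × (2 × 1.008 + 15.999) = 219.50; 65.38 / 219.50 = 29.8%.

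**Step 2. Try to reproduce the stated 80 mg from 83.91 mg of salt**

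- Fraction needed: 80 / 83.91 = 95.3%, against 29.8% or 35.6%. The stated figure is not reproduced under either form.
- Zinc in 83.91 mg: 83.91 × 65.38 / 219.50 = 24.99 mg (dihydrate); 83.91 × 65.38 / 183.47 = 29.90 mg (anhydrous).

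**Step 3. Size of the gap under each reading of the 80 mg**

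| Reading of 80 mg | Compared with | Gap |
|---|---|---|
| Elemental zinc | 24.99 mg (dihydrate) | 80 / 24.99 = 3.20-fold |
| Elemental zinc | 29.90 mg (anhydrous) | 80 / 29.90 = 2.68-fold |
| Loose wording for the salt | 83.91 mg of salt | 83.91 / 80 = 1.049, about 5% |

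Over 14 days the elemental reading gives 80 × 14 = 1,120 mg of zinc, against 24.99 × 14 = 350 mg or 29.90 × 14 = 419 mg.

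**Step 4. Could several units a day explain it?** If 83.91 mg were the content of one unit, 80 mg of zinc would take 3.20 units (dihydrate) or 2.68 units (anhydrous). Neither is a whole number, and no multiple-unit dosing is described.

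**The case against.** The best defence is that this is an editing residue. In the primary objective, the once-daily abbreviation and the comparison phrase each occur twice. Take out the run from the 80 mg parenthesis to the word placebo and a clean sentence is left, which also fits the open-label design without placebo. Study Design shows the same kind of edit with its strike-through intact. A strike-through in the primary objective may have been lost when the PDF was read, or may never have been made; the text does not tell us which. This weakens the only place that says Zn2+ outright.

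The defence goes further. The struck figure in Study Design shows that the authors once wrote 80 mg for the salt, so Study phases may mean the same loosely. On that reading the gap is about 5%. The two formal arm definitions also agree with each other on dose, product and frequency.

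All of this bears on the size of the gap and stands to that extent. It does not remove the conflict. The sentence in Study phases is grammatical and live, and read literally it means elemental zinc. Even read loosely, it gives a different number from the arm definitions.

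A reader might also take the struck figure in Study Design as proof that a change was not carried through. It is not: struck text is superseded, and shows only that the change was made there. The evidence for an incomplete change is the sentence in Study phases.

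**Conclusion.** The inconsistency is real. The arm definitions give 83.91 mg of zinc acetate once daily, Study phases gives 80 mg of zinc, and the primary objective gives both quantities. That 83.91 mg of zinc acetate cannot contain 80 mg of zinc is certain, given standard atomic masses.

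The size of the gap is not certain. It is 2.7- to 3.2-fold if the 80 mg is elemental zinc, which is what the primary objective says and what Study phases says if read literally. It is about 5% if Study phases means the salt and the primary objective's 80 mg is residue.

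Three stronger inferences are not supported. The threefold gap is not established as the only reading. Nothing shows that any patient has received, or is about to receive, a wrong dose, because the documents do not say whether the trial is under way. And the dose does not enter the sample-size calculation, so no stated sample size or power depends on this point. The separate document sent to the Ethics Committee, mentioned under Exclusion Criteria, could not be seen; whether it states the dose is unknown.

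**What to change.** Reconcile Primary objective, Study Design, Study phases and Statistical analysis against the product specification. State the salt form, salt weight, elemental zinc and packets per day once, and use or refer to that statement everywhere the regimen appears. Clear any residual edit text from the primary objective. Report the dose actually delivered when interpreting safety and efficacy and when writing D1.

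This review does not say which figure is right and proposes no dose; that is for the sponsor and investigator to settle from the product specification.

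The cost is small: one look-up, a text correction in four sections, and possibly a notice to the ethics committee. Randomization, sample size and the planned analyses are unaffected.

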Finally, considering the new knowledge that this project will generate about the role of zinc in immune responses and viral expansion, we expect that our results will help researchers and physicians to design novel strategies to boost specific immune cell subpopulations against SARS-CoV2 infection. Thus, this knowledge could be used long-term for designing medicines against SARS-CoV-2 and other viral infections.

- **HYPOTHESIS AND DESCRIPTION OF THE PROJECT OBJECTIVES**

We hypothesize that low zinc nutritional status has an impact on COVID-19 progression and that adjustment of this status might constitute an early therapeutic intervention point by balancing immune responses and acting as an antiviral agent. This hypothesis is supported by the following observations:

- Zinc nutritional status impacts on innate and adaptive immunity and influences inflammatory markers(4).

- Zinc has a direct antiviral activity against specific viruses like rhinovirus, HCV, SARS-CoV(16).

- Zinc supplementation has benefits on the recurrence and persistence of acute and chronic viral infections like common cold, or HCV, HBV (2,6) and reconstitutes the production of interferon-alpha from elderly persons(16).

-Our recent data in a cohort of 249 COVID-19 patients show that COVID-19 patients with lower plasma zinc content have worse prognosis, increased time of hospitalization and mortality and that Zn and IL-6 levels are negatively correlated (13). However, the cause-effect association between nutritional zinc status and COVID-19 inflammatory response remains unproven,

-Our recent data in cell culture studies show that low zinc levels correlate with higher SARS-CoV-2 expansion(13).

The main aim of the project is to explore the therapeutic benefit of Zn supplementation for COVID-19 patients and to determine the cellular and molecular basis of the effect of Zn levels on SARS CoV-2 infections. To address these questions, we propose the following aims:

- **To study the impact of zinc supplementation on COVID-19 progression. There are two specific objectives:**

- **To carry out the clinical trial with COVID-19 patients (Subproject 1):**

We will run a randomized clinical trial with 60 COVID-19 patients admitted at Hospital del Mar with a control and a zinc supplementation group.

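### No rule scores death or discharge for the Week 2 progression endpoint, and the analysis-set and missing-data rules can drop patients because of their outcome

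*Combined protocol and SAP*

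**What the plan says.** **What progression is**

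- *Primary objective*: one aim is to lower the percentage of people with COVID-19 whose disease progresses by Week 2, "defined as inpatients, worsening of" one or more levels on the WHO 9-point scale.
- *Primary Endpoints*: the third entry is "Percentage of patients with disease progression by Week 2 based on WHO 9-point ordinal scale". It gives no threshold and no reference score, and it does not mention inpatients.
- *Task 1.1.2 Assessment of Efficacy*: names the scale. It does not list the levels or say who is scored, when, or how a death or a discharge is handled.

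**Who is analysed (*Statistical analysis*)**

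- *Analysis Populations*: efficacy is per protocol, meaning randomised subjects who finish the two-week course, come back at Week 2, or both.
- *Handling of Dropouts or Missing Data*: dropouts and anyone lacking primary-endpoint data are left out.

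**Who is enrolled and when they are seen**

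- *Hypothesis and description of the project objectives*: the trial takes "60 COVID-19 patients admitted at Hospital del Mar with a control and a zinc supplementation group", so everyone is an inpatient at entry.
- *Study phases*: contacts are planned on Days 7, 14 and 28. The visit list in *Task 1.1.1* does not name the WHO score at any of them.

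**Expected course**

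- *Preliminary Results*: in the sponsor's cohort "23% of the patients had at admission SZC lower than" 50 µg/dl, and the low-zinc group needed "higher time to recover (25 days) versus the control group (8 days"). Whether these are means or medians is not stated.

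**The concern.** The event definition and the endpoint are worded differently, and neither says what happens to this endpoint once a patient dies or goes home. The gap would be cosmetic if the analysis rules kept everyone in. They do not. Completing therapy, returning at Week 2 and having a recorded score all happen after randomisation, and all are related to how the patient fares.

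A patient who dies early has the worst possible course and can leave the analysis. A patient who recovers quickly, goes home, stops early and does not return has a good course and can also leave it. The two losses push the observed rate in opposite directions, and nothing ensures that they balance between arms. Zinc is meant to shorten recovery, and staff know the allocation, so the arms may well differ in how many patients leave and why. Two analysts following the text in good faith could report different progression rates from the same data.

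**Working it through.** **1. The plan's own figures.** "Assuming alpha = 0.05 and a 10% dropout rate", 60 subjects are said to "provide 80% power to detect a difference in time to recovery between arms of 3 days assuming a SD of 4 days".

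- Recovery time: n per arm = 2 × (1.960 + 0.842)² × (4/3)² = 27.9, so 28. Sixty less 10% leaves 27 per arm. Power is then 78.7% by the normal approximation (77.2% by the t-test), within 2 points of the stated figure.
- Progression: the stated power of at least 80% for a 5-point change from 20% does not reproduce. For 20% versus 15% with 30 per arm it is 7.3%. That is a separate problem, and nothing below depends on it.

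**2. Patients traced through the rules as written.**

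| Course to Day 14 | Is it an event? | Is the patient analysed? |
|---|---|---|
| Worsens in hospital, later improves, attends Week 2 | Yes, if the objective's threshold carries over to the endpoint | Yes |
| Dies before the Week 2 visit | Not stated | No: neither finishes therapy nor attends |
| Discharged, worsens outside hospital, attends Week 2 | Depends on what *inpatients* means | Yes |
| Discharged, finishes therapy at home, does not attend | Not stated | In the efficacy set, but excluded if the score is missing |
| Discharged, neither finishes nor attends | Not stated | No |

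**3. How many patients recover before Day 14.** Inputs from *Preliminary Results*: 23% low zinc at 25 days. The other 77% are taken at 8 days, assuming that the control group is everyone else. The distributions are assumptions.

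- Exponential, figures as medians: 0.77 × (1 − 2^(−14/8)) + 0.23 × (1 − 2^(−14/25)) = 0.77 × 0.703 + 0.23 × 0.322 = 0.615.
- Exponential, figures as means: 0.77 × 0.826 + 0.23 × 0.429 = 0.735.
- Normal, SD 4: 0.77 × 0.933 + 0.23 × 0.003 = 0.719.
- Lognormal, figures as medians, log-SD 0.5 to 1.0: 0.697 to 0.613.
- Medians with no shape assumed: at least 0.77 × 0.5 = 0.385, or 23 of 60.

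The range is about 61–73%, or 37–44 of 60. If deaths (5% and 21% in the cohort) never count as recovered, the first figure falls to 0.77 × 0.95 × 0.703 + 0.23 × 0.79 × 0.322 = 0.57.

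**4. What exclusion can do to one arm.** Take the planned control rate, 20% of 30 = 6 progressors with deaths counted among them, and let the plan's 10% dropout be the excluded group, 3 of 30. Both are assumptions about what the plan's figures cover.

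- All 3 excluded had progressed or died: 3/27 = 11.1%.
- None had: 6/27 = 22.2%.

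**5. What a small imbalance in deaths can do.** Cohort mortality gives 0.77 × 5% + 0.23 × 21% = 8.7%, or 2.6 deaths per 30, with timing not given. Suppose both arms truly have 6 of 30, and one death is dropped in one arm and two in the other. The observed rates are 5/29 = 17.2% and 4/28 = 14.3%. The arm with the extra death looks 3.0 points better.

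**The case against.** **The two wordings may not conflict.** The objective's sentence itself counts people with COVID-19, and all patients are admitted at entry, so *inpatients* can simply describe who is enrolled. This stands. A reader might infer that only worsening in hospital counts, contradicting the endpoint. No section says so. The phrase is ambiguous, not restrictive.

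**The denominator is addressed.** *Analysis Populations* admits patients who return at Week 2, which implies that discharged patients can be included. This stands too. A reader might infer a denominator of patients still in hospital on Day 14, which would distort the comparison badly. No section proposes one. What remains is that patients who die, or who neither finish nor return, fall outside the stated set.

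**Recovery is not discharge.** A reader might infer that most patients will have left hospital by Day 14. The cohort figures are times to recover, *Task 1.1.2* defines recovery by clinical signs, and no length of stay is given. Even majority recovery rests on an assumed shape. If nobody in the 25-day group recovers by Day 14, it needs 0.5/0.77 = 65% of the 8-day group to have done so.

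**Losing post-discharge events alone matters little between arms.** This is fair. Let recovery stand in for discharge, take exponential times, and let zinc shorten both medians by 3 days. The share out by Day 14 is then 0.741 against 0.615. With an assumed 3–10% of those patients worsening later, the bias is (0.741 − 0.615) × 3–10% = 0.4–1.3 points.

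**A death is a known outcome, not missing data.** That may answer the missing-data rule, but *Analysis Populations* removes the patient first.

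**Withdrawals are covered elsewhere.** The eligibility section refers to a document sent to the Ethics Committee, which is not available here. It may help, but the analysis rules in this document stand on their own terms.

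**Conclusion.** The concern holds as an ambiguity in wording joined to a gap in scoring. The text does not establish a contradiction between objective and endpoint. Its consequence is that inclusion in a primary endpoint depends on outcome after randomisation.

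The size cannot be fixed from the documents. Dropping a tenth of an arm could move a true 20% to anywhere from 11.1% to 22.2%, and one extra dropped death could shift the comparison by 3.0 points. Both are illustrations, resting on the planned 20% rate including deaths and on assumed numbers excluded. The 61–73% and 38.5% figures show only that recovery before Day 14 should be common enough to need a rule. They are not discharge rates.

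**What to change.** - Use one definition in the *Primary objective* and *Primary Endpoints*: a WHO score at least one level worse than the Day 1 score, at any time from Day 1 to Day 14, in or out of hospital, with death counted as progression.
- Delete *inpatients*, or state that it only describes the enrolled population.
- Analyse this endpoint in all randomised patients, and amend *Analysis Populations* and *Handling of Dropouts or Missing Data* for it.
- Count a patient discharged alive as a non-progressor only if no such worsening occurred before discharge and none is found afterwards up to Day 14. Worsening in hospital stays an event even if the patient then goes home well.
- Score a readmitted patient on the same scale against Day 1. Readmission is not automatically progression.
- Obtain status from the planned Day 7 and Day 14 contacts and from hospital records, and add the WHO score to the visit list.

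The cost is protocol wording and a short status check at contacts already planned. The one downside is that events at other hospitals would rest on patient report.
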